# ANNEX 3: SURVEY ON PRECAUTIONARY HEALTH BEHAVIOUR^1

#### During the last three months,

It really bothers me when people sneeze without covering their mouth

- 0= strongly disagree
- 1= undecided
- 2= strongly agree

I avoid touching door handles and staircase railings at public locations

- 0= strongly disagree
- 1= undecided
- 2= strongly agree

I dislike wearing a face mask

- 0= strongly agree
- 1= undecided
- 2= strongly disagree

I want people's temperature to be taken before they enter public places

- 0= strongly disagree
- 1= undecided
- 2= strongly agree

I don't mind going to very crowded places

- 0= strongly agree
- 1= undecided
- 2= strongly disagree

I would self-isolate myself at home if needed

- 0= strongly disagree
- 1= undecided
- 2= strongly agree

I frequently use hand sanitiser and/or wash my hands after shaking someone's hand

- 0= strongly disagree
- 1= undecided
- 2= strongly agree

I avoid going to public places

- 0= strongly disagree
- 1= undecided
- 2= strongly agree

### **ANNEX 4: STUDY-SPECIFIC COMMON MINIMUM DATASET**

Nr	Variable name		Description	Additional info	Variable format	Values/coding	Mandatory
SITE II	DENTIFICATION						
	idsite		Site identifier		Text	As described in the Study Plan	x
	country		Country identifier		Text	As described in the Study Plan	х
PATIE	NT IDENTIFICATION	I					
	idpatient		Patient identifier	Identifier also contains country and site identifier	Text	As described in the Study Plan	x
	sex		Sex		Numeric (categorical)	1=Male 2=Female X=Sex-neutral	x
	ageyears		Age in years at admission		Numeric		Х
ADMI	SSION DATA						
	onsetdate		Date of first symptom onset		DD/MM/YYYY	Date within the study period	Х
	admissiondate		Date of hospitalisation	First point of contact (arrival at Emergency Department)	DD/MM/YYYY	Date within the study period	x
	SARI		SARI patient		Numeric (categorical)	0=No	х

CIDRIVE

						COVIDRIVE
					1=Yes	
					9999=No information	
					0=No	
	fever	History of fever or measured fever >=		Numeric (categorical)	1=Yes	x
		38°C		,	9999=No information	
					0=No	
	cough	Cough		Numeric (categorical)	1=Yes	x
			, , ,	9999=No information		
					0=No	
	shortbreath	Shortness of breath		Numeric (categorical)	1=Yes	x
	Shortbreath		itumene (euregeneur)	9999=No information	~	
					0=No	
	anos_dysg	Sudden onset of anosmia, ageusia or		Numeric (categorical)	1=Yes	x
	dysgeusia	dysgeusia	Numeric (categorical)	9999=No information	~	
	JSION/EXCLUSION CR	ITERIA				
INCLU					0=No	
	vacc_eligible	zible Eligible for COVID-19 vaccination at Numeric (categorical	Numeric (categorical)	• • • • •		
		time of hospitalisation			1=Yes	
		Communication with patient/Legally			0=No	
	comm	Authorised Representative		Numeric (categorical)	1=Yes	Х
		Autionseu Representative			8888=Not applicable	
					0=No	
	consent	Consent/assent given		Numeric (categorical)	1=Yes	Х
					8888=Not applicable	
					0=Patient	
		If consent is given, who gives the			1=Legally Authorised	
	Consentwho1	consent?		Numeric (categorical)	Representative	Х
					8888=Not applicable	
			In case		- F.F	
			consent/assent			
	Consentwho2		needs to be given by		0=Patient	
		If consent is given, who gives the	both	Numeric (categorical)	1= Legally Authorised	x
	CONSCIEWINGZ	consent?	Parent/tutor/guardi	Rumene (categorical)	Representative	
			an and young		8888=Not applicable	
			patient			
			patient			1

						COVIDRIVE
	consentdate	Date of consent given		DD/MM/YYYY	Date within the study period 8888 = Not applicable	х
	prior_hosp	COVID-19 hospitalisation within 3 months prior to the current admission (excl hospital transfers)		Numeric (categorical)	0=No 1=Yes 9999=No information	Х
	contra_swab	Contra-indication for swabbing		Numeric (categorical)	0=No 1=Yes 9999=No information	х
	other_last_vacc	Received last vaccine dose with other than EMA-approved COVID-19 vaccine brand		Numeric (categorical)	0=No 1=Yes 9999=No information	х
COVIE	D-19 VACCINATION H	IISTORY				
	contra_vacc	Any contraindication for SARS-CoV-2 vaccination	Based on locally used criteria	Numeric (categorical)	0=No 1=Yes 9999=No information	х
	covvaccany1	Received SARS-CoV-2 vaccination dose 1		Numeric (categorical)	0=No 1=Yes 9999=No information	х
	covvaccbrand1	Vaccine brand dose 1		Numeric (categorical)	0 = Vaxzevria ® (AstraZeneca) 1= Janssen (Johnson & Johnson) 2 = Comirnaty ® (Pfizer) 3 = Spikevax (Moderna) 4 = Other 5= Nuvaxovid (Novavax) 6= Spikevax bivalent Original/Omicron BA.1 7=Comirnaty Original/Omicron BA.1 8=COVID-19 Vaccine Valneva 9999 = No information	Х
	covvaccdate1	Date of SARS-CoV-2 vaccination dose 1		DD/MM/YYYY		х
	covvaccany2	Received SARS-CoV-2 vaccination dose		Numeric (categorical)	0=No	Х

				COVIDRIVE
	2		1=Yes	
			9999=No information	
covvaccbrand2	Vaccine brand dose 2	Numeric (categorical)	0 = Vaxzevria ® (Astrazeneca) 1= Janssen (Johnson & Johnson) 2 = Comirnaty ® (Pfizer) 3 = Spikevax (Moderna) 4 = Other 5= Nuvaxovid (Novavax) 6= Spikevax bivalent Original/Omicron BA.1 7=Comirnaty Original/Omicron BA.1 8=COVID-19 Vaccine Valneva 9999 = No information	x
covvaccdate2	Date of SARS-CoV-2 vaccination dose 2	DD/MM/YYYY		х
covvaccany3	Received SARS-CoV-2 vaccination dose 3	Numeric (categorical)	0=No 1=Yes 9999=No information	х
covvaccbrand3	Vaccine brand dose 3	Numeric (categorical)	0 = Vaxzevria ® (Astrazeneca) 1= Janssen (Johnson & Johnson) 2 = Comirnaty® (Pfizer) 3 = Spikevax (Moderna) 4 = Other 5= Nuvaxovid (Novavax) 6= Spikevax bivalent Original/Omicron BA.1 7=Comirnaty Original/Omicron BA.1 8=COVID-19 Vaccine Valneva 9999 = No information	x
covvaccdate3	Date of SARS-CoV-2 vaccination dose 3	DD/MM/YYYY		х
covvaccany4	Received SARS-CoV-2 vaccination dose	Numeric (categorical)	0=No	Х

	1				COVIDRIVE
		4	4	1=Yes	
				9999=No information	
	covvaccbrand4	Vaccine brand dose 4	Vaccine brand dose 4 Numeric (categorical	0 = Vaxzevria ® (Astrazeneca) 1= Janssen (Johnson & Johnson) 2 = Comirnaty ® (Pfizer) 3 = Spikevax (Moderna) 4 = Other 5= Nuvaxovid (Novavax) 6= Spikevax bivalent Original/Omicron BA.1 7=Comirnaty Original/Omicron BA.1 8=COVID-19 Vaccine Valneva 9999 = No information	х
	covvaccdate4	Date of SARS-CoV-2 vaccination dose 4	Date of SARS-CoV-2 vaccination dose 4 DD/MM/YYYY		Х
	covvaccanyx	Received SARS-CoV-2 vaccination dose > + 1 (additional dose numbers will be added following real-life use of COVID- 19 vaccine doses)	added following real-life use of COVID- Numeric (categorical	0=No 1=Yes 9999=No information	х
	covvaccbrandx	Vaccine brand of dose x + 1	Vaccine brand of dose x + 1 Text		Х
	covvaccdatex	Date of SARS-CoV-2 vaccination dose x + 1	Date of SARS-CoV-2 vaccination dose x + 1 DD/MM/YYYY		х
	covvacsource	Source of the COVID-19 exposure information	Numeric (categorica)	1=registry 2=medical record 3= vaccine card 9999=No information	х
сомо	ORBIDITIES/RISK FA				
	asthma	Asthma	Diagnostic codes Asthma and definitions can Numeric (categorical be found in Annex	0=No 1=Yes 9999=No information	х

**C VIDRIVE** 

# CINICRIVE

						0011011
			2			
	lungdis	Lung disease	Diagnostic codes and definitions can be found in Annex 2	Numeric (categorical)	0=No 1=Yes 9999=No information	x
ca	ardiovasc	Cardiovascular diseases	Diagnostic codes and definitions can be found in Annex 2	Numeric (categorical)	0=No 1=Yes 9999=No information	x
h	nypertens	Hypertension	Diagnostic codes and definitions can be found in Annex 2	Numeric (categorical)	0=No 1=Yes 9999=No information	x
	liverdis	Chronic liver disease	Diagnostic codes and definitions can be found in Annex 2	Numeric (categorical)	0=No 1=Yes 9999=No information	x
re	endisease	Chronic renal disease	Diagnostic codes and definitions can be found in Annex 2	Numeric (categorical)	0=No 1=Yes 9999=No information	x
typ	be2diabetes	Diabetes	Diagnostic codes and definitions can be found in Annex 2	Numeric (categorical)	0=No 1=Yes 9999=No information	x
	cancer	Cancer	Diagnostic codes and definitions can be found in Annex 2	Numeric (categorical)	0=No 1=Yes 9999=No information	x
i	immuno	Immunodeficiency or organ transplant	Diagnostic codes and definitions can be found in Annex 2	Numeric (categorical)	0=No 1=Yes 9999=No information	x
HER RISK	FACTORS					
pr	regnancy	Pregnancy	Any trimester at symptom onset	Numeric (categorical)	0=No 1=Yes 9999=No information	x

 						COVIDRIVE
pregn_trim		Pregnancy trimester		Numeric (ordinal)	0=Not applicable 1=First trimester 2=Second trimester 3=Third trimester 9999=No information	x
bmi		Body mass index		Numeric	10 to 55 or 9999=No information	Х
smoking		Smoking status (cigarettes, cigars, pipe, hookah, vaping, e-cigarettes). Not ounting exclusively chewing tobacco or snus.	Smoker: nas smoked	Numeric (categorical)	0=Never-smoker 1=Ex-smoker 2=Occasional smoker 3=Daily smoker 9999=No information	
ltcf_res		Is the patient a long-term care facility resident		Numeric (categorical)	0=No 1=Yes 9999=No information	
hcw		Is the patient a healthcare worker		Numeric (categorical)	0=No 1=Yes 9999=No information	
hcw_patient	I	Is the patient a healthcare worker with direct contact to patients		Numeric (categorical)	0=No 1=Yes 9999=No information	

r					· · · · · · · · · · · · · · · · · · ·	COVIDRIVE
	hcw_covid	Is the patient a healthcare worker with direct contact to COVID-19 patients		Numeric (categorical)	0=No 1=Yes 9999=No information	
	hcw_ltcf	Is the patient a healthcare worker working in long-term care facility		Numeric (categorical)	0=No 1=Yes 9999=No information	
	prev_covid	COVID-19 prior to current episode	I had a previous episode of COVID-19 more than 2 months ago	Numeric (categorical)	0=No 1=Yes, clinical diagnosis only 2=Yes, laboratory-confirmed	
PRECA	UTIONARY HEALTH	BEHAVIOR & VACCINATION ATTITUDE	As measured through below	a precautionary health su	rvey, by summing scores on question	s detailed
	prehb_sneeze	Sneeze	It really bothers me when people sneeze without covering their mouth	Numeric (categorical)	0=strongly disagree 1=undecided 2=strongly agree	
	prehb_touch	Touch	I avoid touching door handles and staircase railing at public locations	Numeric (categorical)	0=strongly disagree 1=undecided 2=strongly agree	
	prehb_mask	Face mask	I dislike wearing face mask because of the way it looks and/or feels	Numeric (categorical)	0=strongly agree 1=undecided 2=strongly disagree	
	prehb_crowd	Crowds	I don't mind going to very crowded places	Numeric (categorical)	0=strongly agree 1=undecided 2=strongly disagree	
	prehb_isolate	Self-isolate	I would self-isolate myself at home if needed	Numeric (categorical)	0=strongly disagree 1=undecided 2=strongly agree	

CIDRIVE

	1 1		1		11	COVIDRIVE
	prehb_sani	Hand sanitiser	I frequently use hand sanitiser and/or wash my hands after shaking someone's hand	Numeric (categorical)	0=strongly disagree 1=undecided 2=strongly agree	
	prehb_public	Public places	l avoid going to public places	Numeric (categorical)	0=strongly disagree 1=undecided 2=strongly agree	
LABO	RATORY					
	swabdate	Date of swabbing		DD/MM/YYYY	Date within the study period. In case of multiple tests with at least 1 positive test result within 14 days prior to hospital admission, take the swab date corresponding to the first positive test result. In case all test results are negative, take the earliest swab date within 14 days prior to hospital admission.	х
	virus1	Laboratory result: SARS-CoV-2		Numeric (categorical)	0=SARS-CoV-2 negative 1=SARS-CoV-2 positive 9999=No information	х
	virus2	Laboratory results: coinfection (in addition to SARS-CoV-2)		Numeric (categorical)	0=No coinfection 1=coinfection 9999=No information	х
	virus1_ext	Laboratory result: pathogen	Alternative to Q49 when multiple pathogens are tested	Numeric (categorical)	0=Negative 1=SARS-CoV-2 2=influenza 3=RSV 4=pneumococcus 5=Other 9999=No information	Х

	-		-			COVIDRIVE
	virus2_ext	Laboratory result: In case of coinfectior second pathogen involved	Alternative to Q50 , when multiple pathogens are tested	Numeric (categorical)	0=No coinfection 1=SARS-CoV-2 2=Influenza 3=RSV 4=Pneumococcus 5=Other 9999=No information	х
	sequenced	Tested for genetic variants		Numeric (categorical)	0=No 1=Yes 9999=No information	
	variant_pangolin	Pangolin lineage name		Alfanumeric (categorical)	Example: B.1.117	
	EPI_ISL_nr	GISAID identification number		Alfanumeric	Example: EPI_ISL_412974	
ADDIT	IONAL HOSPITALISA	TION DATA	·	·		
	icu	ICU admission		Numeric (categorical)	0=No 1=Yes 9999=No information	х
	death	In-hospital death		Numeric (categorical)	0=No 1=Yes 9999=No information	х
	discharge_date	Date of discharge or death		DD/MM/YYYY	Date within the study period	Х
OTHE	R VACCINATIONS					
	fluvacc	Being vaccinated with at least one influenza vaccine within 12 months prior to SARI hospital admission		Numeric (categorical)	0=No 1=Yes 9999=No information	х
	fluvaccdate	Date of influenza vaccination		DD/MM/YYYY		Х
	pneumovacc	Received any pneumococcal vaccination	Any time	Numeric (categorical)	0=No 1=Yes 9999=No information	Х
	pneumovaccdate	Year of pneumococcal vaccination	Latest dose	YYYY		Х
TREA	TMENTS					

			COVIDRIV
pre_prophylaxis_6 mo	Having received anti-SARS-CoV-2 antibody products or other drugs indicated for pre-exposure prophylaxis for SARS-CoV-2 infection within 6 months prior to current hospitalisation	Binary	0=No 1=Yes 9999=No information
pre_prophylaxis_b rand	Brand of latest received anti-SARS-CoV- 2 antibody product or other drugs indicated for pre-exposure prophylaxis for SARS-CoV-2 infection	Numeric (categorical)	0=Kineret (anakinra)* 1=Regkirona (regdanvimab) 2=RoActemra (tocilizumab) 3=Ronapreve (casirivimab / imdevimab) 4=Veklury (remdesivir) 5=Xevudy (sotrovimab) 6=Evusheld (tixagevimab / cilgavimab) 7=Lagevrio (molnupiravir) 8=Paxlovid (PF-07321332 / ritonavir) 9=Other
pre_prophylaxis_d ate	Date of treatment start latest received anti-SARS-CoV-2 antibody product or other drugs indicated for pre-exposure prophylaxis for SARS-CoV-2 infection	DD/MM/YYYY	
post_prophylaxis_ 6mo	Having received anti-SARS-CoV-2 antibody products or other drugs indicated for post-exposure prophylaxis for SARS-CoV-2 infection within 6 months prior to current hospitalisation	Binary	0=No 1=Yes 9999=No information
post_prophylaxis_ brand	Brand of latest received anti-SARS-CoV- 2 antibody product or other drugs indicated for post-exposure prophylaxis for SARS-CoV-2 infection	Numeric (categorical)	0=Kineret (anakinra)* 1=Regkirona (regdanvimab) 2=RoActemra (tocilizumab) 3=Ronapreve (casirivimab / imdevimab) 4=Veklury (remdesivir) 5=Xevudy (sotrovimab)

			COVIDRIV
			6=Evusheld (tixagevimab / cilgavimab) 7=Lagevrio (molnupiravir) 8=Paxlovid (PF-07321332 / ritonavir) 9=Other
post_prophylaxis_ date	Date of treatment start latest received anti-SARS-CoV-2 antibody product or other drugs indicated for post-exposure prophylaxis for SARS-CoV-2 infection	DD/MM/YYYY	
post_symptom	Having received anti-SARS-CoV-2 antibody products or antiviral drugs indicated for treatment post-symptom onset leading to current hospitalisation	Binary	0=No 1=Yes 9999=No information
post_symptom_br and	Brand of received anti-SARS-CoV-2 antibody products or antiviral drugs indicated for treatment post-symptom onset prior leading to current hospitalisation	Numeric (categorical)	0=Kineret (anakinra)* 1=Regkirona (regdanvimab) 2=RoActemra (tocilizumab) 3=Ronapreve (casirivimab / imdevimab) 4=Veklury (remdesivir) 5=Xevudy (sotrovimab) 6=Evusheld (tixagevimab / cilgavimab) 7=Lagevrio (molnupiravir) 8=Paxlovid (PF-07321332 / ritonavir) 9=Other
post_symptom_da te	Date of treatment start anti-SARS-CoV-2 antibody products or antiviral drugs indicated for treatment post-symptom onset leading to current hospitalisation	DD/MM/YYYY	

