#### 15.6.2 SARI patient (possible COVID-19 cases)

A possible COVID-19 case is defined as a hospitalised person with a suspicion of a respiratory infection with **at least one** of the following symptoms:

- cough
- fever
- shortness of breath
- sudden onset of anosmia, ageusia or dysgeusia

with symptom onset within the last 14 days prior to hospital admission as per ECDC definition [10].

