#### 15.6.4 Test-negative control

A study participant that:

• meets the SARI case definition (see 15.6.2)

AND

tests negative for all SARS-CoV-2 RT-PCR or similar molecular assays with specimen(s) collected between 14 days prior to and up to [72 hours] after hospital admission.. Test-negative controls must have a negative result for the RT-PCR or similar molecular assay within [72h] of hospital admission.

 72 hours after hospital admission is the maximum delay accepted for testing. The brand-specific protocol will specify whether the study uses a delay of 24 hours, 48 hours or 72 hours after admission.

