#### 15.14.4.5 Sensitivity analyses

Multiple sensitivity analyses will be performed. In case the RE-MA approach will be adopted, GEE models will be performed as sensitivity. Additional sensitivity analyses will be conducted, exploring the effect of time between symptom onset and swab data and the effects of different SARI case definitions and exclusion of subjects who have received monoclonal antibodies and other anti-SARS-CoV-2 products for either treatment or pre- or post-exposure prophylaxis prior to hospitalisation if there is significant use thereof in the population. Other sensitivity analysis might be conducted when appropriate. All sensitivity analyses will be pre-specified in the SAP.

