**C VIDRIVE** 

# **17 LIMITATIONS OF THE RESEARCH METHODS**

The COVID-19 pandemic is unprecedented, unpredictable and poses challenges for the postmarketing evaluation of the COVID-19 vaccines. The following challenges and limitations for the realworld evaluation of the COVID-19 vaccines have been identified at the time of writing this protocol.

The sensitivity of the SARI case definition is imperfect and potential COVID-19 cases might not be included in the study. This will, however, not bias the CVE estimates unless vaccination affects the presentation of the SARI symptoms. Until now, it is unknown whether COVID-19 vaccination induces a milder course of disease.

As for other epidemiological study designs, the results from TNCC study designs can be biased due to misclassification of disease status using diagnostic assays with imperfect sensitivity and specificity. Low sensitivity and low specificity are expected to bias the CVE estimates downwards with the bias resulting from low specificity being more substantial than the bias from low sensitivity [24]. To minimise misclassification bias, laboratory confirmation based on RT-PCR or another RNA amplification system with at least the same sensitivity and specificity is required for the current study. The specificity of RT-PCR for the diagnosis of COVID-19 is high (>99.5%) while its sensitivity depends on various factors, including timing of sampling, type of specimen and sampling technique. In hospitalised patients, the clinical sensitivity of PCR decreased with days post symptom onset with >90% clinical sensitivity during the first 5 days after symptom onset and 70%-71% from days 9 to 11 [25]. Also, the sensitivity is higher for lower respiratory samples than for upper respiratory tract samples [26], and a good sampling technique is required to obtain better results. To explore any potential bias due to disease misclassification, information on type of specimen will be collected and sensitivity analyses regarding time between symptom onset and swabbing will be performed. Guidance on collecting and handling specimens for the diagnosis of COVID-19 will be given as part of study staff training.

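### Annex 4's single swab-date field does not match the control definition, so the onset-to-swab lag can be negative or falsely short for controls with repeat negative swabs

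*Protocol*

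**What the plan says.** Annex 4 (Laboratory block, variable swabdate) holds one mandatory swab date per patient. With multiple tests and at least one positive in the 14 days before admission, sites must "take the swab date corresponding to the first positive test result". For all-negative patients the rule is: "In case all test results are negative, take the earliest swab date within 14 days prior to hospital admission". Neither rule mentions swabs taken after admission, and no other Annex 4 field holds a swab date.

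Section 15.6.4 defines a control as a SARI patient who "tests negative for all SARS-CoV-2 RT-PCR or similar molecular assays with specimen(s) collected between 14 days prior to and up to [72 hours" (a placeholder for 24, 48 or 72) after admission. It adds a second condition: "Test-negative controls must have a negative result for the RT-PCR or similar molecular assay within" [72h] of hospital admission. Section 15.6.3 uses the same specimen window for cases.

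Section 15.6.2 requires SARI "with symptom onset within the last 14 days prior to hospital admission", so a swab in those 14 days may fall before onset.

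The lag matters because section 15.14.4.5 plans sensitivity analyses "exploring the effect of time between symptom onset and swab data". Section 17 ties these to disease misclassification: "sensitivity analyses regarding time between symptom onset and swabbing will be performed". It cites PCR sensitivity above 90% in the first 5 days after onset and 70% to 71% on days 9 to 11.

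**The concern.** A false-negative control is a missed case, and the risk rises with the time from onset to swab. The lag analysis is the protocol's check on this, and it is informative only if the recorded lag belongs to a test that could have detected the current illness.

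For a case, the rule dates the swab that established the status. For a control it dates the oldest swab available, which may predate the illness. A control whose only post-onset test came late can then appear as short-lag or negative-lag, and a well-timed control can acquire an impossible negative lag.

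The problem lies in what is collected. Section 15.13.1 has sites transform their data locally to the common minimum dataset and upload that. If the relevant date is not a field, a later analysis plan cannot recover it.

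**Working it through.** The protocol states no figure on this point, so there is none to reproduce. The check sets the rules side by side and then sizes the effect under stated assumptions.

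**Range of the lag.** Day 0 is admission, onset runs from day −14 to 0, the earliest swab from day −14 to 0, and a later qualifying swab from day 0 to +3, on or after onset.

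- Stored lag = earliest swab − onset. It runs from −14 − 0 = −14 to 0 − (−14) = +14 days.
- Qualifying lag = qualifying swab − onset. It runs from 0 to 3 − (−14) = 17 days.

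**Worked patients, each with two negative swabs.**

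| Onset | Swabs | Stored lag | Qualifying lag | Comment |
|---|---|---|---|---|
| −10 | −13 and 0 | −3 | +10 | The only post-onset test falls where sensitivity is about 70% |
| −2 | −10 and 0 | −8 | +2 | A well-timed control with an impossible lag |
| −10 | −9 and 0 | +1 | +10 | The early swab is informative, so little harm |

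In the third row, taking 90% sensitivity at lag 1 and 70% at lag 10 and assuming independent tests, the chance that both miss an infection is 0.10 × 0.30 = 0.03. With the late swab alone it is 0.30. A short recorded lag is reasonable for that patient.

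**Illustrative size.** All of the following are assumptions: onset uniform on 1 to 10 days before admission; every control swabbed on admission day; a fraction f with one extra negative swab uniform on 1 to 14 days before admission; a 5-day cut-off. This gives 10 × 14 = 140 equally likely combinations among re-swabbed controls.

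- Stored lag negative (extra swab before onset): the sum over onset day d = 1 to 10 of (14 − d) is 140 − 55 = 85. Share 85/140 = 60.7%.
- Admission-swab lag over 5 days: 5 × 14 = 70 combinations. In 10 of them the stored lag also exceeds 5 days, so 70 − 10 = 60 move to a stored lag of 5 days or less.
- Of those 60, the extra swab falls at lag 0 to 5 days in 5 × 6 = 30. These patients do have an early post-onset negative. In the other 30 (8 + 7 + 6 + 5 + 4) the extra swab precedes onset, so no early post-onset test exists. Share 30/140 = 21.4%.

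| f | Recorded swab before onset (f × 60.7%) | Filed at 5 days or less with no early post-onset test (f × 21.4%) |
|---|---|---|
| 10% | 6.1% | 2.1% |
| 30% | 18.2% | 6.4% |
| 50% | 30.4% | 10.7% |

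The rest of the first column (at 30%, 18.2 − 6.4 = 11.8 points) is controls with an admission swab within 5 days of onset who nevertheless get a negative lag. If every extra swab were taken on or after onset, both columns would be zero.

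**The case against.** Four points count on the other side.

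First, a reader might take the whole shift in recorded lag as damage. In the model at 30% re-swabbing, the share with lag over 5 days falls from 50% to 0.7 × 50% + 0.3 × 7.1% = 37%. That overstates the harm: half of the shifted combinations (30 of 60) have a real negative within 5 days of onset, so only about 6.4 of the 12.9 points reflect wrong filing. This stands.

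Second, the wrongly filed controls all carry a negative lag. Section 16.4 provides central checks for implausible values and inconsistent variables, which could flag them. This stands in part: a query can expose the problem, but no field exists to hold the correct date.

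Third, the protocol fixes no 5-day cut-off or restricted analysis and leaves the detail to the analysis plan. This stands, and it is why the figures are only illustrative. It does not rescue the date rule, since any lag analysis needs a valid lag.

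Fourth, a reader might infer that patients are misclassified or that the primary estimate is biased. The documents do not support that. Status follows sections 15.6.3 and 15.6.4 and has its own result field, and section 15.14.4.3 models calendar time by symptom onset date.

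Two further limits apply. Controls with a single swab present no choice between dates. If within [72h] of admission also covers the hours before it, an early swab in that span may itself qualify, though any older one is still stored in its place.

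**Conclusion.** The inconsistency is real and should be corrected. As written, the Annex 4 rule can store a date that precedes the illness and is not that of the swab required by section 15.6.4. Its multiple-test rules also omit the post-admission window that sections 15.6.3 and 15.6.4 allow. Read literally, the all-negative rule gives no date to a control swabbed only after admission.

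The reach is narrow: the onset-to-swab sensitivity analysis, and central verification of the qualifying negative where an earlier swab is the one stored. The primary vaccine effectiveness estimate is not affected.

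The size cannot be determined from the protocol. The illustration of about 18% of controls with a recorded swab before onset, and about 6% wrongly filed as short-lag, rests on the assumed 30% re-swabbing, the even spread of earlier swabs, the onset distribution and the 5-day cut-off. If repeat tests are mostly prompted by symptoms, both figures shrink towards zero.

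**What to change.** - Define swabdate over the window of sections 15.6.3 and 15.6.4: 14 days before to [72 h] after admission.
- For cases, store the first positive swab.
- For controls, store the first negative swab on or after symptom onset.
- Add a field for the date of the qualifying negative swab within [72h] of admission. Alternatively, store all swab dates and results.
- Compute the onset-to-swab lag from post-onset swabs only.

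Dating every control by the admission swab alone would not be a good substitute. It would discard an earlier post-onset negative, such as the one in the third worked patient, and record a well-tested control as long-lag.

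The cost is a wording change in Annex 4 and the site data dictionary, plus one extra date. Sites already hold that date, because they need it to classify a patient as a control.

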# **15.3 Study population**

The study population consists of individuals (patients), presenting at the participating hospitals during the study period, who

• meet the inclusion criteria (see Section 15.3.1) but who do NOT meet the exclusion criteria (see Section 15.3.2).

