# 15.4 Study period

#### « Modify as appropriate »

From month 202[X], with a minimum duration of 12 months and an expected duration of two years

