#### 15.6.3 Test-positive case

A study participant who:

• meets the SARI case definition (see Section 15.6.2)

AND

tests positive in at least one SARS-CoV-2 RT-PCR or similar molecular assays with specimen(s) collected between 14 days prior to and up to [72 hours] after hospital admission.

 72 hours after hospital admission is the maximum delay accepted for testing. Each brand-specific protocol will specify whether the study uses a delay of 24 hours, 48 hours or 72 hours after admission.

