# **16.4** Data quality checks at central level

An automatic data quality check will be done during data upload to the COVIDRIVE Research Serve (CRS) via the EDTA. The data quality checks relate to compliance with the study-specific common minimum data requirements (Annex 4), the presence of duplicated records, variable formats, implausible values, inconsistencies between variables and missing values. All uploaded data will be checked again for quality by the P95 team. If data quality issues are found, the study site data responsible person will be contacted, and the data will either be corrected or discarded from further analysis. After performing the data quality checks and implementing the corrective measures, the study inclusion criteria will be applied and records with missing data in the outcome and/or exposure information will be discarded.

For every study site separately, a data quality report will be produced. This report will contain a description of the results of the quality checks performed, the amount of data that was retained for analysis after applying the inclusion criteria and graphical summaries of the retained data. The data quality report will be sent to the site for approval.

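### Annex 4 confines onset, swab and discharge dates to the study period, which contradicts the eligibility windows and the length-of-stay definition; if enforced, it would reject some early patients and lose the longest late stays

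*Protocol*

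**What the plan says.** Time eligibility in section 15.3 rests on one event: patients "presenting at the participating hospitals during the study period". Section 15.6.2 admits patients "with symptom onset within the last 14 days prior to hospital admission". Sections 15.6.3 and 15.6.4 accept specimens "collected between 14 days prior to and up to" a bracketed 72 hours after admission. Section 15.9.3 measures stay in nights from admission to discharge or death. It sets no end-of-study limit and adds together stays for readmissions within 3 months.

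Annex 4 sets the accepted values. For `onsetdate`, `admissiondate` and `discharge_date` the entry is "Date within the study period". The `swabdate` cell begins "Date within the study period. In case of multiple tests with at least 1 positive test result within 14 days prior to hospital admission", so one cell carries both the study-period limit and the pre-admission window. All four fields are mandatory. `discharge_date` has no code for missing information or for a patient still in hospital, whereas `icu` and `death` have 9999.

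Section 16.4 checks uploads automatically against Annex 4. Where issues are found the site is contacted and "the data will either be corrected or discarded from further analysis". Section 15.4 leaves the start date as a placeholder, "with a minimum duration of 12 months and an expected duration of two years".

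**The concern.** An eligible patient can have a true date that the dataset does not accept. A patient admitted on study day 3 with onset 5 days earlier meets section 15.6.2, but the onset date precedes the study. A patient admitted 10 days before study end and discharged after 30 nights meets section 15.3, but the discharge date falls 20 days after the end.

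The consequences differ at the two ends. At the start, eligible patients may be lost. At the end, only stays that finish before the closing date have an acceptable discharge date. If the others are dropped, length of stay is right-truncated and the lost stays are the longest. That bears on exploratory objective 5 in section 14.3. Since this is the master from which requestor-specific and site-specific protocols are made, and section 15.13.1 has every site transform its data to the Annex 4 format, the ranges would be copied into each study.

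**Working it through.** The protocol gives no figure for length of stay or onset delay, so there is nothing to reproduce. The study lengths and the 14-day windows come from the protocol. The stay distributions, delays and admission patterns are assumptions.

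**Do the rules fit for any choice of dates?** The same term, study period, governs who may enter (15.3) and which dates are accepted (Annex 4). Moving the start earlier or the end later also admits new patients at the new boundary, and they meet the same problem. Only separate rules for admission and for the other dates remove it.

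**Start of study.** With uniform admissions over T days, the share with onset before day 0 is about (mean onset-to-admission delay)/T, and cannot exceed 14/T.
- Ceiling: 14/365 = 3.8%; 14/730 = 1.9%.
- Assumed mean delay 3 to 7 days: 3/365 = 0.8% to 7/365 = 1.9% at 12 months; 0.4% to 1.0% at two years.

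This is a loss of patients. It does not depend on how long they stay, so it does not by itself bias length of stay.

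**End of study.** Let L be the stay, with mean m and coefficient of variation CV. A record is kept only if admission + L ≤ T. With uniform admissions:
- share dropped ≈ m/T
- mean of dropped stays ≈ E[L²]/m = m(1 + CV²)
- mean of kept stays ≈ (T·m − E[L²])/(T − m)

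For m = 10, CV = 1, E[L²] = 200:
- T = 365: dropped 10/365 = 2.7%; dropped mean 20 nights; kept mean (3650 − 200)/355 = 9.72, or −2.8%.
- T = 730: dropped 1.4%; kept mean (7300 − 200)/720 = 9.86, or −1.4%.

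Other assumptions:

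| Scenario | T = 365 | T = 730 |
|---|---|---|
| Log-normal, log SD 0.8, mean 10.5 nights | −2.7% | −1.3% |
| Range over mean 5–20, CV 1–1.5 | −1.4% to −13% | −0.7% to −6.3% |
| Mean 10, CV 1, admissions 3–5 times as frequent in last 60 days | −6.5% to −8.9% | −3.6% to −5.3% |

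**Long ICU stays** (assumed mean 25.5 nights, log SD 0.8, T = 365). Share dropped 25.5/365 = 7.0%. Simulation gives a mean of about 47 nights for the dropped stays and 23.9 for the kept stays, about −6%. The closed form, with 1 + CV² = exp(0.64) = 1.896, gives 48 nights and (9307.5 − 1233.2)/339.5 = 23.8, or −6.7%. The simulation rounds stays up to whole nights, which accounts for the small gap.

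**Between-group contrast**, the target of exploratory objective 5 (assumed true means 12 and 8, CV 1). At T = 365 the kept means are 11.59 and 7.82: the difference falls from 4.00 to 3.77 and the ratio moves from 0.667 to 0.675. At T = 730 they are 11.80 and 7.91: difference 3.89, ratio 0.670.

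**The case against.** The strongest reply is that this is loose wording in a template. Section 16.4 allows correction as well as discarding. The record-level removals it names are for failing the inclusion criteria or lacking outcome or exposure information, and a discharge date is neither exposure nor primary outcome. The `swabdate` cell itself expects tests from before admission, so the phrase was probably not meant to cancel that window. The study period is a placeholder, length of stay is one optional exploratory objective, and handling of open stays is ordinary content for a statistical analysis plan.

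Much of this stands, and it rules out several stronger readings.
- A reader might infer that length of stay is biased. The documents support only that it would be if the range check acts as a filter.
- A reader might apply the rule to each interim data cut. Annex 4 refers to the study period, and no text extends the rule to a cut.
- A reader might infer differential loss by vaccine exposure, or between cases and controls. Either would need assumptions about brand timing or onset delays that the protocol does not supply.
- A reader might infer that the description of critical cases loses its severe patients. That description rests on ICU admission and the Annex 1 form, so it suffers only if whole records are deleted.

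Two parts of the reply fail. The placeholder does not help, because the same term governs enrolment. Correction does not help either, because a true date outside the range has nothing to be corrected to, and `discharge_date` offers no code for an open stay.

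**Conclusion.** The contradiction is in the text and needs no assumption. Its consequence is conditional on enforcement and modest in size. The early loss is capped at 3.8% of patients at 12 months and 1.9% at two years. Mean stay over all patients would fall by roughly 3% and 1.4% respectively under a mean of about 10 nights and uniform admissions. Larger falls need long or skewed stays or a wave at the end. The contrast in exploratory objective 5 barely moves when truncation acts on both groups alike, and the effect on primary vaccine effectiveness is small. The reason to act is that the rule is wrong as written, would be inherited by every derived protocol, and is almost free to put right.

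**What to change.** In Annex 4:
- Keep the study-period limit for `admissiondate` only.
- Accept `onsetdate` from `admissiondate` minus 14 days to `admissiondate`.
- Accept `swabdate` from `admissiondate` minus 14 days to `admissiondate` plus the chosen 24, 48 or 72 hours.
- Accept `discharge_date` at any date after `admissiondate`, in line with the overnight-stay definition, with no study-end limit. Add a code for patients still in hospital.
- Treat stays open at data lock as censored, and do not discard them.

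With these ranges, the share rejected by the date rules and the resulting truncation of stay are both zero. The cost is three range edits, the matching change to the upload check, and either a short wait before final lock or a censored analysis. Because section 15.9.3 adds readmissions within 3 months, complete episodes may take longer than the last discharge, which favours censoring over waiting.
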